The Use of Mentoring to Promote Well-being for Female SMART Members

NCT04247880

June 23, 2025

Study Protocol

Significance

Construction workers are exposed to numerous chemical and physical hazards, leading to risks such as slips, trips and falls, musculoskeletal disorders, electrocution, and other chronic and acute health outcomes. Younger workers entering apprenticeships must learn to work around these chemical and physical hazards safely, but also contend with psychosocial hazards such as bullying and hazing. High job demands coupled with low control and lack of support at work also contribute to worker stress and risk of injury. For workers with children, balancing the long and unpredictable work hours with their family's needs can be stressful, a burden placed disproportionately on women workers. For underrepresented workers, there is additional vulnerability due to a culture that often condones harassment and discrimination based on gender and race. The percentage of women in the industry remains dismally low: 3% of workers nationally are women. Tradeswomen's minority status directly contributes to their risk for negative mental and physical health outcomes, as well as their burnout rates, thereby creating a negative feedback problem.

Employment of construction and extraction occupations throughout the country is projected to grow 11% from 2016 to 2026, faster than the average for all occupations. However, demand for skilled tradespeople is far outpacing supply due to national shortages of skilled construction labor and gaps in the apprenticeship pipelines. Because of low apprentice retention rates and underrepresentation of women in the industry, there is a growing recognition among unions, contractors, and public owners of the importance of women to meeting current and future demands. Assuring that women, particularly the younger workers entering the trades as apprentices can learn to work safely and retain jobs in the industry is a high priority for the industry. Lating

Building on mentorship and leadership curricula from the UW research group. Sheet Metal Workers Locals 16 and 66, and CPWR, we will design a mentorship training program to be delivered online in both synchronous (live webinars) and asynchronous (viewing previously developed or recorded materials on their own time) modalities. Journey-level workers from each intervention local will be recruited and trained to be mentors to women in their affiliated apprenticeship programs. Mentees in the intervention arm will be recruited and paired based on mutual preference with mentors within their local in two waves, allowing for at least two years of follow-up for each mentee. Women apprentices in the control locals will be recruited to participate in the evaluation only. Evaluation will assess changes in safety advocacy, selfefficacy, as well as work experience (including exposure to physical and psychosocial hazards), health (stress related indices), safety (injury experience and risk-avoidance actions) and retention in the trade. Evaluation will utilize pre- and post-program questionnaires and calculate retention rates for women apprentices in affiliated apprenticeship programs. In addition, interviews with mentors will add to a process evaluation. Using the developed curriculum and mentorship programs, and results of the evaluation, we will produce a guide to effective mentorship for women in the trades, and, in conjunction with CPWR, disseminate the materials widely. Locals participating in the program as controls will be provided with the training for any journey-level members interested in becoming mentors after the final evaluation is completed.

To help guide the development, implementation and results interpretation and dissemination, we will establish a program advisory board, who will meet annually with the research team throughout the project period. The board will include [name], Assistant to the General President of SMART, [name], Chair of the Women's Committee for SMART Local 66, [name], researcher for CPWR, a representative of the sheet metal contractors' association, TBN, an expert on mentorship for women in the trades ([name], Instructor with SMART Local 16), and a professor of construction management ([name]).

Recruitment and Assignment of Locals

UW researchers will work with SMART to identify locals to participate in the study, based on availability and membership size. Among the 81 Sheet metal worker JATCs, there are currently a total of 461 women apprentices, however they are not evenly distributed. Twenty-six locals have five or more women apprentices, so we will focus our efforts on the locals with a sufficient number of women to support our training and evaluations. Leaders at each local will receive information about the study and descriptions of the intervention. We will invite each local with 5 or more women apprentices to participate in the study. We will then rank order them by size, and randomize them to control or intervention groups, within size categories.

We will identify a key staff member at each local or apprenticeship program to serve as our primary on-site Mentorship Coordinator for the participant recruitment, training delivery, and mentorship programming. The identification of this person will be up to each local, but could be the apprenticeship coordinator, or instructor, a women's committee member, or a local safety coordinator, or staff person.

[figure not shown]

Figure 3. Study research design

Development and Delivery of Training

Mentor training provided to participants will draw content from the UW and Locals 16 and 66 programs, the CPWR Foundations for Safety Leadership curriculum, as well as other evidence-based mentor training materials. The goal of the training is to increase women's knowledge of, and self-efficacy and skills in safety advocacy to reduce their injury risk, as well as psychological stressors at work. The training is grounded in principles of social support, most notably emotional, informational and appraisal support that mentors can provide. The training will focus on: active listening, asking effective questions, two-way communication, understanding how construction culture affects women apprentices' health and safety, types of social support, mentorship benefits, setting goals, identifying barriers to success, and cultivating mentee problem-solving and self-advocacy skills. We will also provide mentors with resources for addressing mentee challenges that are outside the scope of the program (e.g., housing insecurity, domestic violence, etc.), adapted from resources available in the union's location.

Delivery of the training: The training model will include multiple modalities in order for it to be delivered effectively to remote locations. It will include written materials and exercises which can be reviewed or completed individually, and webinar style presentations by our training expert. Most importantly, it will include synchronous workshops that will discuss key components of effective mentoring, and provide opportunities for mentoring practice, and discussions and problem-solving with input from the trainer.

The synchronous training sessions will be implemented with internet-based conferencing software such as Zoom or Skype, linking classrooms at each training location with the trainer. Based on other mentorship training programs, we project that we will need two synchronous training sessions, each lasting four to six hours. Prior to the first training, we will assign materials for review, and low-stakes "homework" assignments for exploration between the two sessions. In addition, we will follow-up with each Mentorship Coordinator to provide any additional guidance or practice needed.

All components of the mentorship training will be piloted with members of the advisory board and other local SMART volunteers, and revised prior to implementation. Each component of the training will be delivered to a group of volunteers, and subsequently discussed with the study team for revision.

Recruitment of Mentors and Mentees

Once the locals have been assigned to intervention or control, UW researchers will work with the identified Mentorship Coordinator at each intervention local to identify potential mentors and mentees. Mentors will be journey-level workers with the interest and capacity to support up to four mentees over the four years. While preferable to have women mentors for women apprentices, we will allow journeymen with an interest in the program if there are insufficient numbers of available journeywomen. Each potential mentor will receive a description of the purpose of the project, and a full outline of the commitment of time and effort involved in their participation, including compensation. Mentors will sign informed consent letters approved by the UW IRB.

Eligible mentees at intervention locals will be women currently enrolled in an affiliated apprenticeship program, with at least two years left prior to expected completion, and who are at least 18 years old. We will work with the Mentorship Coordinator and the Apprenticeship Coordinator at each local to provide recruitment materials, and informed consent letters to all eligible apprentices. Although we don't anticipate a problem with over-subscription to the program, if this occurs, we will allow the local to determine if they prefer to add mentors to accommodate the demand, or to restrict participants to a manageable number.

At control locals, we will work with the Apprenticeship Coordinator to recruit women apprentices, 18 years or older, with at least two years expected prior to journeying-out. Control apprentices will similarly sign informed consent letters to participate in the evaluation questionnaires.

Program Support

A key component of effective mentorship programs is allowing prospective mentees to find mentors with whom they have a level of trust. We will foster such pairing by sponsoring a "meetup" at each intervention local, at which each mentor will introduce her/himself, and provide time for mentees to meet individually with each potential mentor. Mentees will subsequently inform the Mentorship Coordinator of their first and second choice for mentors, and we will assist the Mentorship Coordinator in making final pairs assignments. Mentees and Mentors will be free to decline the assignment, or request a change at any time in the program.

Each mentor will be contacted by our staff for a follow-up 'check-in' once quarterly. The purpose of these check-ins is several-fold. The check-in will provide an opportunity for the project staff to remind the mentors of the need to actively engage the mentee at regular intervals. Second, the check-in is a chance for 'refresher' training on key components of effective mentoring. It also provides an opportunity to help identify and solve any challenges that come up in the mentoring relationship - either transactional, or substantive - that is providing suggestions for additional resources. Finally, the check-in will form a component of the process evaluation (see below) to monitor the progress of the program and any barriers to its success.

Delivery of Mentorship Training to Control Locals

Because we have prior expectations that the mentorship program will have some degree of success, we don't want to withhold any benefits from the control locals. Thus, we will repeat the mentorship training with control locals in year five of the project. Participation will be voluntary, and no evaluation of the training will be included in this. Rather, it will be a service to the contributing local unions and their members.

Evaluation and Analysis

We have developed the following logic model of the mentorship program to describe our program and provide guidance on necessary evaluation components.

Inputs	Activities	Outputs	Short-term	Intermediate	End Outcomes
			Outcomes	Outcomes	
UW mentorship	Recruit women	Mentor-	Increase in	Reduction in	Reduced
program	apprentices	mentee interact	awareness of	perceived stress	injuries
	and mentors	on regular basis	safety & health		
Sheet Metal			risks	Increase in self-	Improved jobsite
Workers Locals	Online mentor	Mentors provide		advocacy	safety climate
16 and 66	training	emotional,	Increase in self-	behaviors	
programs		appraisal, &	efficacy		Increased
	Matching	informational		Increase in	representation of
CPWR	mentors to	support to	Improved self-	problem-	women in trade
Leadership	mentees	mentees	advocacy	solving skills	
training			knowledge		
programs	Ongoing			Increase in job	
	program		Improved social	satisfaction	
Local union	support		support at work		
engagement				Increased retention	
				in apprenticeship	
				and trade	
PLANNED WORK			RESULTS		

This logic model shows the program inputs and outputs. We will conduct both process and impact evaluations, as described below. We will measure short-term, intermediate term and long-term outcomes, however, we hypothesize that short and intermediate outcomes will be affected by our mentorship program.

Analysis plan

We will conduct a hypothesis-driven analysis of the primary outcome (perceived stress) and a limited set of secondary outcomes that we highlighted as especially important in the grant.

Research question & hypotheses

Primary research question: What is the effect of the mentorship intervention on apprentice's **perceived stress**? Hypothesis: expect a reduction in perceived stress among the intervention group (mentees) compared to controls

Secondary research questions: What is the effect of the mentorship intervention on the following **short-term and intermediate outcomes**: social support at work, job satisfaction, and intention to leave construction trades? Hypothesis: expect an improvement (increase) in these outcomes among the intervention group compared to controls

Other (process and longer-term health) outcomes we will consider in a second paper where we'll conduct a more exploratory analysis by group:

- Self-reported health
- Self-reported mental health
- Sleep quality
- Sought professional help for mental health
- Sickness presenteeism
- Physical activity outside work
- Insomnia
- Depression severity
- Anxiety severity
- Work/life conflict
- Demand/control
- Overcompensation
- Bullying
- Age discrimination
- Race discrimination

- Gender discrimination
- Tokenism
- Sexual harassment
- Injury at work
- Work injury severity
- frequency of being understood
- perceived effectiveness at communicating
- self-advocacy behaviors
 - formal skills training
 - goal setting
 - perceived progress towards goals
 - perceived ability to advocate for own needs on jobsite

Data

Two control (total n = 40) and intervention (total n = 56) cohorts surveyed at three timepoints each: baseline, 6 months, and 1 year.

Subset of 18 control and 16 mentees who completed surveys at all three timepoints.

Variables to be used in descriptive analysis

Demographics by group:

- Age
- Race/ethnicity

- Marital status
- Family annual income
- Education
- Years in construction industry

Baseline variables by group:

- Mentor experience
- Mentor type
- Formal mentorship training
- Local level mentorship

Variables to be used in primary analysis

Exposure: group – 0 for control, 1 for intervention

Outcome: perceived stress score (continuous)

Fixed effects: time, group x time

Random effect: union local

Covariates: age, race/ethnicity, family annual income, year in apprenticeship, size of local,

region of the country

Variables to be used in secondary analyses

Exposure: group – 0 for control, 1 for intervention

Secondary outcomes: Social support at work (continuous), Job satisfaction (continuous),

Intention to leave construction trades (categorical)

Fixed effects: time, group x time

Random effect: union local

Covariates: age, race/ethnicity, family annual income, year in apprenticeship, size of local,

region of the country

Statistical methods

Software: R

Analysis of loss to follow-up

Compare those who dropped out to those who stayed in study by:

- Union local [tally]
- Race/ethnicity
- Age
- Marital status
- Dependents
- Stress at baseline
- Years in construction industry
- Intervention status [yes/no]

- Round
- Intention to leave construction industry
- Difficulty taking time off during work to take care of personal or family matters
- Frequency of interference between job demands and family life or personal time
- Frequency of interference between family demands and work

And/or model for loss of follow up to include group, round, plus other vars listed above

Use chi-square test of independence (for discrete variables)/Fisher's Exact test (for count data, small sample sizes)/t-test (for continuous variables)/Wilcoxon rank sum test (for continuous variables not normally distributed)

Bivariate analysis

With same tests as above, compare demographic and other sample characteristics by arm at baseline

With same tests as above, compare primary and secondary outcomes by arm at baseline, midyear, and end-year; also do by round

With same tests as above, do same comparison for subset of respondents in each arm who have surveys at all three timepoints; also do by round

Graph observations (averages, error bars). Spaghetti plots showing trajectories for each person, by group. Stratify by group, explore change btw timepoints. Either paired t-test or single rank Wilcoxon test. First compare BL to MY, then MY to EY.

Multivariate analysis

From research strategy: To evaluate changes over time, effectiveness of the intervention will be analyzed using a mixed effects regression model. For our primary outcome (perceived stress scale, PSS), a base model will be developed with PSS as a function of arm (intervention/control), and survey (pre, 6 months, post), with a random effect for local union (to assess difference between locals, and to control for non-independence within locals). We will then test the contributions of additional co-variates, including demographics, year in apprenticeship, size of local, and region of the country, etc. Co-variates will be retained if they are statistically significant (p<0.1) or change the coefficient for study arm by \geq 10%. Similar models will subsequently be run for each short-term and intermediate outcome.

Table shells -> see SMART Training Program_Survey responses + table shells_17Jun24.xlsx

Table 1: Baseline characteristics of participants (n=X), by study arm [+ outcomes at baseline for descriptives, may not use]

Table 2: Effect of mentorship training on level of perceived stress among tradeswomen using mixed effects regression models; base model + models with added covariates, in stages

Table 3: Effect of mentorship training on [X secondary outcomes] among tradeswomen using mixed effects regression models; base model + models with added covariates, in stages

Notes

Keep track of remaining tasks and questions here. Update with steps taken and info obtained as tasks are completed.

Survey data

Estimated missingness for each variable.

Filled in sources as best as I could in scale source doc.

Data dictionary – For scores that we modified, proposed strategy (mostly should just be average score, but noted any alternatives reported in the literature, e.g. if others that are unaltered but just subset of questions and whether others have done that, whether they standardized the scale to the original i.e. by multiplying total by old max divided by new max).

SMART Women_Variable info – summarizes variables we plan to analyze, their type (demographic/confounder, outcome, mediator) and how they'll be categorized.

Working list of analytic steps to do in R

Conduct descriptive analysis of demographic characteristics by study arm (intervention/control) using relevant statistical test. Also check balance in terms of year in apprenticeship, size of local, and region of the country.

Analysis of loss to follow-up:

- Union local size [tally cioè of n ppl in local?]
- Race/ethnicity
- Age
- Marital status
- Dependents [y/n]
- Stress at baseline
- Years in construction industry
- Intervention status [group]
- Round
- Intention to leave construction industry
- Difficulty taking time off during work to take care of personal or family matters
- Frequency of interference between job demands and family life or personal time
- Frequency of interference between family demands and work

Visualize outcomes by group at each time point --> did this implicitly by running tests automatically in crosstables. If outcomes not normally distributed, compare groups at each timepoint (not differences) using Wilcoxon ranksum test (rather than two sample t-test). Complete responses. Will tell us if have group diffs at each timepoint.

once have dates, edit code and add to plots by round (all data, complete responses)

From research strategy: To evaluate changes over time, assess effectiveness of the intervention using a mixed effects regression model. For our primary outcome (perceived stress scale, PSS), we envision a base model with PSS as a function of arm (intervention/control), and survey

(baseline, 6 months, and 1 Year), with a random effect for local union (to assess difference between locals, and to control for non-independence within locals). We then envision testing the contributions of additional co-variates, including demographics, year in apprenticeship, size of local, and region of the country. Co-variates will be retained if they are statistically significant (p<0.1) or change the coefficient for study arm by \geq 10%. We envision running similar models run for each short-term and intermediate outcome.

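### With 65% of women missing a survey, a model with a random effect for local only can bias the 1-year arm effect if loss depends on earlier stress and completion, or that dependence, differs by arm; the loss analysis has no stated use.

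*Combined protocol and SAP*

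**What the plan says.** The Data section gives "Two control (total n = 40) and intervention (total n = 56) cohorts surveyed at three timepoints each: baseline, 6 months, and 1 year", and then a "Subset of 18 control and 16 mentees who completed surveys at all three timepoints".

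For the primary and secondary outcomes, the variable lists give "Fixed effects: time, group x time" and "Random effect: union local". The Multivariate analysis section and the closing notes describe a base model of arm and survey, also with local as the only random effect and with no interaction stated. No section has a term for the participant.

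Under Bivariate analysis, after comparing outcomes by arm at each survey, the plan will "do same comparison for subset of respondents in each arm who have surveys at all three timepoints".

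Under Analysis of loss to follow-up, it will "Compare those who dropped out to those who stayed in study by" a list that includes baseline stress, intervention status and intention to leave, and adds: "And/or model for loss of follow up to include group, round, plus other vars listed above". It does not say what follows from either. Covariates stay in the outcome model if p is below 0.1 or if they move the arm coefficient by at least 10%, not because they predict loss. No missing-data assumption, imputation, weighting or sensitivity analysis is stated.

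**The concern.** A likelihood-based mixed model can accommodate loss that depends on a woman's observed earlier scores, but only if it models the correlation among her own scores. With local as the only random effect, two scores from one woman are treated as no more alike than scores from two women in the same local. The 1-year estimate is then close to a comparison of whoever answered, and is safe only if loss is nearly unrelated to stress. The between-arm comparison of the 34 completers has the same weakness.

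The programme aims to lower stress and raise retention, so a link between stress and loss is plausible. The plan itself lists baseline stress as something to compare between dropouts and stayers. If stressed mentees are lost more often, the remaining mentees look less stressed, and the bias takes the direction of the hypothesised benefit. The loss analysis might reveal this, but the plan gives it no way to correct the estimate.

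**Working it through.** **1. Counts (Data section).**
- Missing at least one survey: (40 - 18) + (56 - 16) = 22 + 40 = 62; 62/96 = 64.6%.
- Completion: control 18/40 = 45.0%; intervention 16/56 = 28.6%; difference 16.4 points.
- Standard error: sqrt(0.450 × 0.550/40 + 0.286 × 0.714/56) = 0.099. 95% CI: 16.4 ± 1.96 × 9.9 = -3.0 to 35.9 points. Fisher's exact p = 0.13.

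The documents give no percentage, power or bias figure to reproduce.

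**2. What the local-only model ignores.** Assume, since the documents give no variances, 5% of variance between locals, 50% between women and 45% residual. Two scores from one woman then correlate at 0.05 + 0.50 = 0.55, and scores from two women in one local at 0.05. The planned model has a single parameter for both.

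**3. Simulation with no true effect.** Score = local + woman + residual, with the variances above and about 4 women per local. The log-odds of being a non-completer is a(arm) + b(arm) × baseline stress in SD units, with a(arm) set so that completion is 45.0% and 28.6%. The bias is the estimated group × 1-year coefficient. Two patterns for non-completers are used, because the documents do not say which surveys were missed: all gave baseline only, or equal thirds gave baseline only, baseline plus 6 months, and baseline plus 1 year.

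Bias in SD, local-only model:

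| Slope b, intervention / control | Interaction, baseline only | Interaction, equal thirds | Arm coefficient without interaction, baseline only |
|---|---|---|---|
| 1 / 1 | -0.07 | about 0 | -0.03 |
| 1 / 0.5 | -0.16 | -0.05 | -0.07 |
| 1 / 0 | -0.29 | -0.10 | -0.12 |
| 0 / 1 | +0.23 | +0.12 | +0.10 |

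Repeat runs gave -0.07 to -0.08, -0.15 to -0.18, -0.28 to -0.29 and +0.19 to +0.24 for the first column, and +0.10 to +0.12 for the last row of the second. With both slopes 0, the bias was 0.00. With equal slopes and equal completion it was -0.002.

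**4. Completers only.** The bias in the arm difference at 1 year was -0.09, -0.20, -0.30 and +0.26 SD for the same four rows.

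**5. Different assumptions.** A second simulation let loss at each visit depend on the previous score, with no return after a missed survey, local correlation 0.03 and an odds ratio for loss of 2 per SD. With within-woman correlation 0.5 or 0.7, the local-only bias was -0.08 or -0.10 (same in both arms), -0.26 or -0.37 (intervention only) and +0.19 or +0.27 (control only). So a stronger within-woman correlation enlarges the bias.

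**6. With a participant intercept added.** The interaction bias was within about 0.02 SD of zero in every scenario of both simulations. That model was given the true variances, and loss depended only on observed scores.

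**The case against.** Several objections stand in part.

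- **The pattern of gaps is unknown.** The 62 women include anyone who missed a single survey, even if she answered at 1 year. Under the equal-thirds pattern the bias falls to about half or less. That split is as arbitrary as the baseline-only one, so a range is the fair statement.
- **Dependence on stress alone is not enough.** With equal slopes and equal completion the bias vanishes. It needs unequal completion, which p = 0.13 leaves compatible with chance, or a slope that differs by arm, for which the documents give no evidence. But an interval of -3.0 to 35.9 points does not establish equal completion either.
- **Precision is poor anyway.** With 96 women in 24 locals of 4, the simulated sampling SD of the 1-year contrast is about 0.33 SD (baseline only) or 0.26 SD (equal thirds). A bias of 0.08 is about a quarter of 0.33 (0.08/0.33 = 0.24); one of 0.29 is close to it (0.29/0.33 = 0.88).
- **The reported coefficient may be the arm main effect.** The base model states no interaction, and its arm coefficient has less than half the bias in the table.
- **Completer tests are already secondary.** They sit under Bivariate analysis, and the effect tables use mixed models. A label is all that is needed.

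A reader might infer that attrition in this trial is known to be stress-related, or that the result is biased toward benefit. The documents support neither: they report no link between stress and loss, and the direction depends on the arm in which any link is stronger.

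**Conclusion.** The concern holds in conditional form. The plan omits the correlation among a woman's own scores, has 65% of women with a missing survey, and gives its loss analysis no role in the outcome model. If loss depends on earlier stress, and completion or that dependence differs by arm, the 1-year group-by-time effect is biased under no true effect.

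With 5/50/45% variances and a log-odds of loss of 1 per SD of baseline stress, the size is about 0 to -0.08 SD for equal dependence, -0.10 to -0.29 SD for dependence in the intervention arm only, and +0.10 to +0.23 SD in control only. The larger figures assume that non-completers gave baseline only. It would be too strong to say that any dependence on stress biases the effect, or that a participant intercept settles the matter: the intercept does not cover loss driven by a woman's unobserved current stress. The change is worth making because it is cheap and removes an avoidable exposure of the primary estimate.

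**What to change.** In the primary and secondary variable lists, the Multivariate analysis section and the closing notes:

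1. Add a random intercept for participant nested in local, with the matching mixed model for the categorical outcome (intention to leave), and use all available surveys.
2. State that this analysis assumes loss depends only on observed data.
3. Label the comparisons in the 34 completers as descriptive.
4. Add a sensitivity analysis by multiple imputation that respects participant and local, shifting missing intervention-arm PSS by increasing amounts until the conclusion changes.
5. Do not choose covariates by testing dropouts against stayers; with 96 women, such tests miss real predictors. Baseline stress, arm and local are also on that list but already enter the model. If predictors of loss are added, prespecify a short list of baseline variables not already in the model.

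Cost: no new data. The model is slightly more complex, and there is one extra sensitivity table. The imputation for clustered repeated scores is the main extra work.

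### Recruitment round is left out of the primary and secondary outcome models, although the plan uses it in its dropout analysis, by-arm outcome comparisons and plots

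*Combined protocol and SAP*

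**What the plan says.** **Two waves.** The Overview under Approach has intervention mentees recruited "in two waves, allowing for at least two years of follow-up for each mentee". The Data section gives both arms two cohorts: "Two control (total n = 40) and intervention (total n = 56) cohorts surveyed at three timepoints each". It adds: "Subset of 18 control and 16 mentees who completed surveys at all three timepoints". Neither count is split by round.

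**Randomisation.** Under Recruitment and Assignment of Locals, locals are ranked by size and the plan will "randomize them to control or intervention groups, within size categories". Round is not named as a stratification factor.

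**Where round is used.**
- Analysis of loss to follow-up: round is one of the listed comparisons, and the plan adds "And/or model for loss of follow up to include group, round, plus other vars listed above".
- Bivariate analysis: the plan will "compare primary and secondary outcomes by arm at baseline, midyear, and end-year; also do by round", and do the same for women with all three surveys.
- Working list of analytic steps: "once have dates, edit code and add to plots by round".

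**Where round is absent.** The variable lists for the primary and secondary analyses give group as exposure, "Fixed effects: time, group x time", a random effect for union local, and six covariates (age, race/ethnicity, income, year in apprenticeship, size of local, region). The narrative under Multivariate analysis describes a base model of arm and survey with a random effect for local, then tests further covariates. It keeps those with p<0.1 or a change of at least 10% in the arm coefficient. Round is not named there, although that list is left open-ended. The restatement that closes the Notes gives the same list as a closed one.

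**The concern.** The plan treats round as worth examining for dropout and for outcome differences, but leaves it out of the models that give the treatment estimate. Randomising locals within size categories does not hold the wave mix equal across arms. Women are recruited after their local has been assigned, and by different routes: intervention women join a mentoring programme whose numbers a local may restrict, while control women join only the evaluation.

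If perceived stress differs between waves and the arms draw differently from them, part of the wave difference can be read as an arm effect. Running the bivariate comparisons by round does not adjust the model estimate. Under the retention rule, round would enter only if someone chose to test it and it passed a data-driven threshold.

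**Working it through.** The plan states no power, effect size or SD, so it has no figure of its own to reproduce. Effects below are in SD units of the outcome.

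**Inputs from the documents.** 56 intervention and 40 control women; 16 and 18 with all three surveys.

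**Assumed inputs.** Round mix by arm, size of the round effect *d*, and retention by round. The documents give none of these.

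**1. Arm coefficient of the base model (arm + survey).**
- Bias = (share in a given round, intervention minus control) × *d*.
- With 65% v 35%: 0.30 × 0.2 = 0.06; 0.30 × 0.3 = 0.09; 0.30 × 0.5 = 0.15 SD.
- Wider range: mix differences of 0.1 to 0.4 and *d* of 0.2 to 0.8 give 0.02 to 0.32 SD. With equal mix the bias is 0.
- For scale, the simple standard error is √(1/56 + 1/40) = √0.04286 = 0.207 SD, ignoring clustering. The value 0.15 is 0.15/0.207 ≈ 0.7 standard errors.

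**2. Group-by-time model.** Here the arm term is the baseline difference and the interaction compares change from baseline. A stable round effect with a stable mix shifts every timepoint equally, so it drops out of the interaction. What remains is
- bias in group × time = *d* × [change in round share from baseline to follow-up, intervention minus control].

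Illustration: 28 intervention women per round, 4 of 28 (14%) retained in one and 12 of 28 (43%) in the other, which sums to the 16 completers. The second round's share moves from 0.50 to 12/16 = 0.75. If the control share stays put and *d* = 0.5, bias = 0.5 × 0.25 = 0.125 SD.

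**3. Simulation check of the group-by-time model.** 1,500 runs per scenario; 20 locals with rounds crossed; variances 0.05 local, 0.50 person and 0.45 residual; *d* = 0.5; no true arm effect; dropouts miss both follow-ups; random effect for local only.

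| Scenario, round omitted | Arm term | Group × time, 1 year | Arm difference, 1 year |
|---|---|---|---|
| Equal mix, dropout unrelated to round | 0.00 | −0.01 | −0.02 |
| Mix 70% v 50%, dropout unrelated to round | 0.09 | 0.01 | 0.11 |
| Equal mix, intervention retention 14% v 43% by round | 0.00 | 0.12 | 0.11 |

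Monte Carlo standard errors are 0.006 to 0.009. With round as a fixed effect, every entry is within about 0.02 of zero.

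**4. Is differential dropout plausible?** Completion was 16/56 = 28.6% v 18/40 = 45.0% (Fisher p = 0.13), and 34/96 = 35.4% overall. Attrition is heavy enough to allow it, but nothing shows how it fell by round.

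**5. Gain if there is no bias.** With an even split, round contributes variance *d*²/4, which is 0.01 for *d* = 0.2 and 0.0625 for *d* = 0.5. That is about 1% to 6% of the total, so adjusting cuts the standard error by about 0.5% to 3%.

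**The case against.** The strongest reply is that the models quoted contain group × time, and in that term a stable wave difference largely cancels. This stands. Under the 65% v 35% mix with *d* = 0.5, simulation puts 0.155 SD in the arm term and −0.004 in the interaction. The 0.06 to 0.15 SD therefore belongs to the arm coefficient of the base model, and to any arm difference read off at a single timepoint. It does not belong to the interaction.

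The dropout route can bias the interaction, but the retention figures used to show it are assumed. Part of that bias also reflects a separate omission: adding a random effect for participant, without round, roughly halved it in a rerun (0.13 to 0.07 SD).

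It can also be said that the open-ended covariate list under Multivariate analysis admits round, and that the 10% rule targets this kind of confounding. That is partial cover only. The rule acts on whatever is chosen for testing, and the restatement in the Notes has no open ending.

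Some stronger readings are tempting but unsupported:
- That 56 v 40 shows a wave imbalance. Unequal arm totals say nothing about the mix within each arm, and both arms have two cohorts.
- That every bivariate test is split by round. The instruction attaches to the outcome-by-arm comparisons, not to baseline characteristics or to the paired tests over time.
- That the by-round comparisons waste precision. They are additional, and the unsplit tests and the mixed model remain.
- That round is already coded. The working list is still waiting for dates.

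**Conclusion.** The omission is confirmed: round is in neither model specification nor among the named candidate covariates. Its consequence is conditional. A reader might infer that the treatment effect is confounded by wave. The documents do not support that, because they give no round-by-arm counts and no round effect.

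The base-model arm coefficient is exposed if the wave mix differs by arm, by 0.06 to 0.15 SD under the stated assumptions, which is at most about 0.7 of a simple standard error. The group-by-time term is exposed mainly if dropout differs by round and arm, by about 0.12 SD in the assumed example. If neither condition holds, the bias is zero and the precision gain is small. Reading round as recruitment wave is itself an inference, since the plan does not define the term. This is a cheap improvement and not a serious flaw.

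**What to change.** - Define round as recruitment wave.
- Report the number of women by round, arm and timepoint, so that any imbalance in entry or retention is visible.
- In the variable lists for the primary and secondary analyses, add round as a prespecified fixed effect, exempt from the p<0.1 or 10%-change rule. Make the narrative under Multivariate analysis and its restatement in the Notes agree.
- A round-by-time term can be a sensitivity analysis.
- The by-round comparisons may stay as supplementary; whether to test them formally is a matter of preference.

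The cost is SAP wording, one degree of freedom per model, and confirming survey dates so that round can be coded.
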